### **1.5 STUDY DESIGN RATIONALE**

This Phase IIa study is designed to establish the safety and tolerability of DA-9805 compared to placebo in subjects with PD. This study will also seek to determine the effectiveness of DA-9805 in subjects with PD, which will provide information for subsequent clinical trials with DA-9805.

### **1.6 RISKS AND BENEFITS**

The safety monitoring practices employed by this protocol are adequate to protect the subjects' safety and should detect all Treatment Emergent Adverse Events (TEAEs). The approximate volume of blood ( $\sim$  60-75 mL) planned for collection from each subject over the course of the entire study presents no undue risk to the participants. An indirect health benefit to the subjects enrolled in this trial is the free medical tests received at screening and during the study.

## 2 STUDY OBJECTIVES

- To evaluate the safety and tolerability of DA-9805 at 45mg, 90mg compared to Placebo (0 mg) in subjects with Parkinson's disease.
- To evaluate DA-9805 at 45mg, 90mg compared to Placebo (0 mg), in terms of efficacy in subjects with Parkinson's disease.

### 3 STUDY DESIGN

This is a phase IIa, first in human, randomized, double-blind, multicenter study to evaluate the safety, tolerability and efficacy of DA-9805 at 45mg, 90mg versus placebo in subjects with early diagnosed Parkinson's disease.

The study will include three parts: a 2-week Screening part, a 12-week Double-Blind Treatment part, and a 4-week Follow-up part. The Schedule of Events is provided in [Table 4-1](#).

#### Study Visits:

- **Screening Visit** (Day -14 to Day -1), up to 14 days:

Screening part is designed to determine subject's eligibility to proceed to Randomization and the Treatment Phase of the study. During this part, a series of assessments will be performed to determine subject eligibility as per inclusion and exclusion criteria.

At the Screening Visit, prior to any study-related procedures, a written informed consent will be obtained from the subject by the Investigator or suitable qualified personnel. Screening procedures will be conducted per the study schedule of events ([Refer to section 4.1.1](#)). All screening information will be documented in the case report forms.

Subjects who meet eligibility criteria, but have some abnormal laboratory values, based on PI review a repeat laboratory sample may be collected. The repeat laboratory reports should be reviewed by the PI to confirm eligibility prior to randomization.

Subjects who fail to meet eligibility criteria during the Screening part will be considered screen failures and will be exited from the study. Subjects who have successfully completed the Screening part will enter the Double-Blind treatment part of the study. Treatment part followed by randomization will last for 12 weeks. Subjects will take the randomized treatment, DA-9805 at 45mg, 90mg or placebo for 12 weeks.

- **Visit 0: Randomization/Baseline Visit** (Day 0) (TV0): On Day 0 prior to randomization, the subject's continued eligibility will be evaluated ([Refer to section 4.1.2](#)). Subjects who continue to be eligible will be randomized in a 1:1:1 ratio to one of the following treatment groups and assigned the study treatment kit:

- Group 1: DA-9805 45mg tablet
- Group 2: DA-9805 90mg tablet
- Group 3: placebo (0 mg DA-9805) tablet

DA-9805 and matching placebo are oral tablets that will be taken three times daily during this study.

- **Treatment Visits 1 (TV1) through Treatment Visit 3 (TV3):**

[figure not shown]
Clinic treatment visits TV1 through TV3 will be conducted every four (4) week ( $\pm$  3 days). During each of these visits, study evaluations will be conducted per the study schedule of events ([Refer to section 4.1.3](#)), and sufficient supply of DA-9805 or placebo till the next treatment visit will be dispensed.

Treatment Visit 3 (TV3) will be considered the end of treatment (EOT) clinic visit. Study evaluations, review of the adverse events and concomitant medications and final study treatment accountability will be conducted.

- **Follow-up Part (4 weeks  $\pm$  3 days)**

The follow-up part will consist of a follow-up visit at the end of the Double-Blind Treatment part.

The detailed study schedule and assessments in each visit are provided in [Section 4.1](#) of the protocol.

**Figure 3-1: Study Flow Diagram**

### 3.1 STUDY POPULATION

#### 3.1.1 NUMBER OF SUBJECTS

A total of 60 subjects will be randomized to this study from up to 10 Centers within the USA.

### 3.1.2 INCLUSION CRITERIA

Subjects will be eligible for enrollment in the study only if they meet ALL of the following criteria:

1. Male or female subjects who are between 30 and 79 years old inclusive with a clinical diagnosis of Parkinson's disease as per UK Brain Bank Criteria for two (2) years or less at screening.
2. Hoehn and Yahr I or II at screening.
3. Subjects who are newly diagnosed & currently not on any Parkinson's disease medication (or) subjects who are on stable doses for at least 4 weeks prior to screening on Amantadine or anticholinergics for treatment of Parkinson's disease.
  1. Note: Subjects that had anti-parkinsonian medication (including levodopa, dopamine agonists, entacapone and monoamine oxidase-B inhibitors) discontinued at least 60 days prior to screening, e.g., for intolerance, may be considered eligible if all other eligibility requirements are met.
4. Women of child-bearing potential should use reliable contraception. Acceptable methods of contraception include: surgical sterilization (e.g. bilateral tubal ligation), hormonal contraception (implantable, patch, and oral), and double-barrier methods (condom, diaphragm and spermicide are each considered a barrier). Women of child-bearing potential are defined as women physiologically capable of becoming pregnant, UNLESS they meet the following criteria:
  1. Post-menopausal: 12 months of natural (spontaneous) amenorrhea or 6 months of spontaneous amenorrhea with serum Follicle Stimulating Hormone (FSH) levels  $> 40\text{mIU}/\text{m}$ , OR;
  2. 6 weeks post surgical bilateral oophorectomy with or without hysterectomy
5. If a male and heterosexually active with a female of childbearing potential, the subject must agree to use a double barrier method of birth control (or must have been surgically sterilized) and to not donate sperm during the study.
6. Without clinically significant abnormalities in physical exam, neurological exam and laboratory assessments (urine/blood routine, biochemical tests and ECG) which would exclude the subject from the study in the opinion of the Investigator. For Aspartate aminotransferase (AST), alanine aminotransferase (ALT) and alkaline phosphatase (ALP) the screening levels should be  $\leq 2$  times upper limit normal.
7. Subject is capable of providing informed consent and is willing to sign the ICF prior to study Screening and agrees to comply with the study protocol requirements.

### 3.1.3 EXCLUSION CRITERIA

Subjects will be eligible for enrollment in the study only if they meet NONE of the following criteria:

1. Subject has an atypical parkinsonian syndrome or secondary parkinsonism (e.g., due to drugs, metabolic neurogenetic disorders, encephalitis, cerebrovascular disease or degenerative disease).
2. Subjects with history of neurosurgical intervention for Parkinson's disease.
3. Subjects who meet the DSM-V criteria at screening for bipolar disorder, major depressive disorder, psychotic disorders, or any other comorbid mental disorders that in the opinion of the Investigator may interfere with study conduct and results interpretation.
4. Subjects with clinical diagnosis of dementia (MMSE score  $<24$ ) as determined by the investigator using Mini-Mental State Examination (MMSE).
5. Female subjects who are pregnant or breast feeding.

6. Initiation of any anti-parkinsonian medication (including levodopa, dopamine agonists, entacapone and monoamine oxidase-B inhibitors) for the duration of the trial.
7. Initiation of Amantadine or anticholinergics for newly diagnosed subjects or change in the dosage of Amantadine or anticholinergics during the trial for subjects who were on stable doses for 4 weeks prior to screening.
8. Subjects who used investigational drugs or devices within 60 days prior to screening or investigational biologics within the last 6 months prior to screening.
9. Subjects with a clinically significant medical or surgical condition, including major surgeries within 28 days prior to enrollment.

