### 4.1.2 TREATMENT VISIT 0 (TV0): RANDOMIZATION/BASELINE VISIT (DAY 0)

If continued to be eligible for the study at TV0, the subject will proceed to be randomized. All entrance criteria must be met prior to randomization of a subject into the protocol. The following assessments will be performed:

Treatment Visit 0 (TV0) – Prior to Randomization: Perform the following baseline assessments

- Assessment of continued eligibility (Refer to [Section 3.1.2](#) and [Section 3.1.3](#))
- Medical history (Refer to [Section 8.4](#))
- Vital signs (Refer to [Section 8.5](#))
- Body Weight (Refer to [Section 8.6](#))
- Physical Examination (Refer to [Section 8.7](#))
- Electrocardiogram (Refer to [Section 8.9](#))
- Urine pregnancy test (Refer to [Section 8.10](#))

- MDS-UPDRS Scale (Refer to [Section 8.11](#))
- Hoehn and Yahr (H&Y) Scale (Refer to [Section 8.12](#))
- Schwab and England (S&E) Scale (Refer to [Section 8.15](#))
- Parkinson's Disease Questionnaire (PDQ-39) total score (Refer to [Section 8.13](#))
- Clinical Global Impression-Severity (CGI-S) scale (Refer to [Section 8.14](#))
- List concomitant medications (Refer to [Section 7](#))
- Columbia-Suicide Severity Rating Scale (C-SSRS) (Refer to [Section 8.16](#))
- Mini-Mental State Examination (MMSE) (Refer to [Section 8.17](#))
- Randomization (Refer to [Section 9.4](#))

Treatment Visit 0 (TV0) – Post Randomization: Perform the following assessments

- Vital signs (Refer to [Section 8.5](#))
- Study treatment dispensation (Refer to [Section 6.7](#))
- Study treatment first dose administration (Refer to [Section 6.7](#))
- Adverse events evaluation after first dose (Refer to [Section 10](#))

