## 8.10 URINE PREGNANCY TEST

The result must be documented on the source documents and in the CRF. Subjects who are found to be pregnant during the screening period will be considered a screen failure. If pregnancy occurs during the course of the study, the subject will be withdrawn from the study and the pregnancy will be followed up to term for safety purposes. Relevant safety information collected after the study has completed will be reported as supplemental information.

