### 8.16 COLUMBIA-SUICIDE SEVERITY RATING SCALE (C-SSRS)

The Columbia Suicide Severity Rating Scale (C-SSRS) is a widely used suicidal ideation/suicidal behavior assessment tool (Posner, 2011). The C-SSRS assesses both suicidal ideation and suicidal behavior using questions in eleven (11) categories: five (5) for suicidal ideation, five (5) for suicidal behavior, and one (1) for self-injurious behavior without suicidal intent. There is a binary response (yes/no) for each question. For the purpose of this study, the “Lifetime/Recent” version of the C-SSRS, including questions spanning subjects’ lifetime as well as the one (1) month prior to screening will be used as the baseline evaluation. On the following visits the “Since Last Visit” version of the C-SSRS will be used to assess the treatment-emergent suicidal ideation/behavior under study treatment. Suicidal ideation or behavior is defined as a “yes” answer to any one of the 10 suicidal ideation or behavior questions on the C-SSRS. All ratings will be done by a trained interviewer and ideally by the same individual at each study site. Examples for both versions of the C-SSRS to be used are depicted in the text [Figure 18-1](#) and text [Figure 18-2](#).

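### No entry criterion excludes on suicidality itself, so a subject with a recent attempt or ideation with intent, and no qualifying disorder, can be randomized in full compliance with the protocol

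*Protocol*

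**What the plan says.** Entry is decided by the criteria in Protocol sections 3.1.2 and 3.1.3, which the synopsis repeats. Section 8.2 ties the eligibility assessment to those lists. Section 4.1.2 makes them the gate at TV0: "All entrance criteria must be met prior to randomization of a subject into the protocol".

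Two exclusions come near the subject of suicide risk:

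- Exclusion 3 covers bipolar disorder, major depressive disorder and psychotic disorders by DSM-V, and then "any other comorbid mental disorders that in the opinion of the Investigator may interfere with study conduct and results interpretation".
- Exclusion 9 reads "Subjects with a clinically significant medical or surgical condition, including major surgeries within 28 days prior to enrollment".

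The C-SSRS is scheduled at screening, at TV0 before randomization, and at TV1 to TV3 (Table 4-1, sections 4.1.1 to 4.1.3). Section 8.16 says of the Lifetime/Recent form that it "will be used as the baseline evaluation", and has later visits use the Since Last Visit form. It counts a yes to any of the 10 ideation or behavior questions as positive, but gives no action for a positive answer before randomization. Section 9.10.2 of the protocol and section 8.3.2 of the SAP provide only listings and descriptive summaries.

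**The concern.** The protocol asks about suicidal ideation and behavior twice before the first dose and then makes no use of the answers at the point where they could protect the subject. An investigator with a positive C-SSRS in hand could randomize without committing a deviation. Whether that happens is left to individual judgment at up to 10 sites.

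The main stake is subject safety. DA-9805 has not been given to humans before (section 1.4), and a subject already known to be at risk would start it and go home until TV1.

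A lesser stake is the safety data. Change in C-SSRS is a listed safety outcome, and the Since Last Visit form is meant to pick up suicidality arising on treatment. One subject already suicidal at entry is 1/20 = 5% of an arm and would make that information hard to attribute.

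**Working it through.** The plan states no figure on this point. The check is a reading of the criteria, one count and one interval.

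**1. What each criterion tests**

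| Inclusion (3.1.2) | Exclusion (3.1.3) |
|---|---|
| 1 Age, diagnosis and its duration | 1 Atypical or secondary parkinsonism |
| 2 Hoehn and Yahr stage | 2 Neurosurgery for Parkinson's disease |
| 3 Antiparkinsonian medication | 3 Mental disorders |
| 4 Contraception, women | 4 Dementia, MMSE below 24 |
| 5 Contraception, men | 5 Pregnancy or breast feeding |
| 6 Physical and neurological exam, laboratory, ECG | 6 Starting antiparkinsonian drugs |
| 7 Consent and compliance | 7 Starting or changing amantadine or anticholinergics |
| | 8 Recent investigational products |
| | 9 Medical or surgical condition |

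Total: 7 + 9 = 16. Number naming suicidal ideation, suicidal behavior or a C-SSRS result: 0.

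**2. Whether a near criterion reaches the case by its terms.** Take a subject with a recent attempt or ideation with intent whom the investigator does not judge to have a mental disorder.

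- Exclusion 3: not met. The named part needs a DSM-V diagnosis. The discretionary part still needs a mental disorder, and its test is interference with conduct and interpretation.
- Exclusion 9: not met, unless the attempt left a clinically significant medical or surgical condition.
- Inclusion 6: satisfied. It lists examinations, laboratory tests and ECG, and the C-SSRS is not among them.
- Inclusion 7: satisfied if the subject can consent and agrees to comply.

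Section 9.4 then says that consenting subjects who meet all inclusion and no exclusion criteria will be randomized.

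**3. Whether the information exists in time.** On the Lifetime/Recent form in Appendix 5, ideation is recorded for lifetime and the past month, and behavior for lifetime and the past 3 months. The TV0 administration is listed among the procedures before randomization. Both results are therefore available when the decision is made.

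**4. How other screening results are treated.** An MMSE below 24 excludes (exclusion 4). AST, ALT and ALP must be no more than 2 times the upper limit of normal (inclusion 6). For pregnancy, which is exclusion 5, section 8.10 adds the consequence: "Subjects who are found to be pregnant during the screening period will be considered a screen failure". The C-SSRS has neither a threshold nor a stated consequence.

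**5. Interval to the next scheduled check.** Section 3 says "Clinic treatment visits TV1 through TV3 will be conducted every four (4) week", and section 4.1.3 sets TV1 at Day 28 ± 3. With the first dose on Day 0:

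- earliest: 28 − 3 = 25 days
- latest: 28 + 3 = 31 days

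No visit or C-SSRS is scheduled in between.

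**The case against.** The case on the other side is that the gap is narrow and other duties cover it. Most people with a recent attempt or intent to die will be judged to have a disorder that falls under exclusion 3, whose last clause is not limited to named diagnoses. The criteria say subjects are eligible only if they meet them, which is a necessary condition and not an order to enrol. Investigators are also bound by GCP, the Declaration of Helsinki and the Belmont principle of beneficence (sections 8.1, 14 and 14.2). After entry there are unscheduled visits (4.3), repeat C-SSRS at TV1 to TV3, best-interest withdrawal (5.2) and a DSMC (12). The visit interval applies to every subject. No drug signal is reported, and the primary endpoint and its analysis are unaffected.

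Much of this stands. The existing criteria probably remove many at-risk subjects, a careful investigator would likely decline the rest, and no frequency can be given. It does not close the gap. The general duties leave the decision unstandardized across sites, section 9.4 is worded more strongly than a necessary condition, and every safeguard in sections 4.3, 5.2 and 12 acts only after randomization. It is also true that no document supplies a C-SSRS entry threshold, so the cut-off proposed below is a clinical choice.

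**Conclusion.** The concern holds. By their terms, 0 of 16 criteria exclude on suicidality, although the C-SSRS is completed twice before randomization. A subject with a recent attempt or ideation with intent and no qualifying disorder or condition is eligible as written, with the next scheduled check 25 to 31 days after the first dose.

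This rests on reading exclusions 3 and 9 as written, so that each requires a disorder or condition to be judged present. It does not assume that DA-9805 raises suicide risk, or that any given number of the 60 subjects would be affected; the documents support neither statement. The change is worth making because it protects subjects in a first-in-human study at little cost. It has no bearing on the efficacy analysis.

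**What to change.** Add one exclusion to section 3.1.3 and to the synopsis:

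> Any suicidal behavior in the past 3 months, or suicidal ideation with intent (C-SSRS ideation item 4 or 5) in the past month, at screening; or either on the Since Last Visit form at TV0 before randomization.

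The look-back periods are those of the Lifetime/Recent form. The sponsor's medical lead should confirm the threshold and may make it stricter, for example by applying the any-yes definition of section 8.16 over the same periods.

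No visit, assessment or analysis is added, because the C-SSRS is already done at both time points. The cost is a protocol amendment touching two places and some extra screen failures. Their number cannot be estimated from the documents, and it would be at least as high under the any-yes rule.

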## 4 STUDY SCHEDULE

The schedules for the protocol-specified assessments and procedures for this study are detailed in this section. Day 0 is used as the day of Randomization/baseline and first randomized study treatment administration. See [Table 4-1](#).

**Table 4-1: Study Schedule of Events**

Study Parts	Screening Part (2 weeks)	Double-Blind Treatment Part (12 weeks)					Follow-up Part Follow-up Visit(4 weeks)
		TV0 Randomization		TV1	TV2	TV3	
Treatment Visits		Day 0					FUV
Weeks from Randomization Date (window period: ± days)	- 2	Pre-		Post-	+ 4 (± 3)	+ 8 (± 3)	+ 12 (± 3)
Written Informed Consent	X						
Inclusion/Exclusion Criteria	X						
Schedule Randomization Day	X						
Continued Eligibility		X					
Randomization		X					
Demographics	X						
Medical History	X	X					
Physical Examination	X	X		X	X	X	
Vital Signs	X	X	X	X	X	X	
Height  and Weight	X	X				X	
ECG	X	X		X		X	
Serum Hematology 	X			X	X	X	
Serum Chemistry 	X			X	X	X	
Urine Analysis 	X			X	X	X	
Urine Pregnancy Test 	X	X				X	
MDS-UPDRS		X		X	X	X	
H & Y	X	X		X	X	X	
S & E		X		X	X	X	
PDQ-39		X		X	X	X	
CGI-S and CGI-I 	X	X		X	X	X	
C-SSRS	X	X		X	X	X	
MMSE	X	X					
Dispense the DA-9805 or placebo 			X	X	X		
DA-9805 or Placebo first dose administration			X				
Study treatment accountability				X	X	X	

Study Parts	Screening Part (2 weeks)	Double-Blind Treatment Part (12 weeks)				Follow-up Part Follow-up Visit(4 weeks)	
Treatment Visits		TV0 Randomization		TV1	TV2	TV3	FUV
Weeks from Randomization Date (window period: $\pm$ days)	- 2	Day 0		+ 4 ( $\pm$ 3)	+ 8 ( $\pm$ 3)	+ 12 ( $\pm$ 3)	+ 16 ( $\pm$ 3)
Adverse Events			X	X	X	X	X
Concomitant medications	X	X		X	X	X	X

 Height only at Screening.

 Subjects who meet eligibility criteria, but have some abnormal laboratory values, based on PI review a repeat laboratory sample may be collected. The repeat laboratory reports should be reviewed by the PI to confirm eligibility prior to randomization.

 Only for female subjects of childbearing potential.

 CGI-I will be done only at Treatment Visit 1 to Treatment Visit 3

 Dispense the DA-9805 or placebo at each of the clinic treatment visit, except TV3 which is the End of Treatment visit (EOT).

## 4.1 SCREENING AND RANDOMIZATION

### 4.1.1 SCREENING VISIT (DAY -14 TO DAY -1), UP TO 14 DAYS

The subject will sign and date the ICF, and Health Insurance Portability and Accountability Act (HIPAA) authorization (according to site practices) prior to any study-related procedures. A subject number will be assigned to each subject in successive order of consent signing at each center, beginning with 001 at each site. Each study site will receive a unique numeric designation, and will precede the subject number (e.g. at study center 01 the first two consented subjects would be 01-001 and 01-002; at study center 02 the first two consented subjects would be 02-001 and 02-002).

Screening Visit procedures are per below:

- Informed Consent will be obtained prior to any study-related procedures. (Refer to [Section 8.1](#))
- Eligibility assessment per the inclusion and exclusion criteria and diagnosis confirmation (Refer to [Section 3.1.2](#) and [Section 3.1.3](#)).
- Subject demographics (Refer to [Section 8.3](#))
- Medical history (Refer to [Section 8.4](#))
- Vital signs (Refer to [Section 8.5](#))
- Height, Weight and BMI (Refer to [Section 8.6](#))
- Physical examination (Refer to [Section 8.7](#))
- List concomitant medications (Refer to [Section 7](#))
- Laboratory assessments (hematology, biochemistry and urine analysis) (Refer to [Section 8.8](#))
- Electrocardiogram (Refer to [Section 8.9](#))
- Urine pregnancy test (Refer to [Section 8.10](#))
- Hoehn and Yahr (H&Y) Scale (Refer to [Section 8.12](#))
- Columbia-Suicide Severity Rating Scale (C-SSRS) (Refer to [Section 8.16](#))
- Clinical Global Impression-Severity (CGI-S) scale (Refer to [Section 8.14](#))
- Mini-Mental State Examination (MMSE) (Refer to [Section 8.17](#))
- Schedule randomization visit

### 4.1.2 TREATMENT VISIT 0 (TV0): RANDOMIZATION/BASELINE VISIT (DAY 0)

If continued to be eligible for the study at TV0, the subject will proceed to be randomized. All entrance criteria must be met prior to randomization of a subject into the protocol. The following assessments will be performed:

Treatment Visit 0 (TV0) – Prior to Randomization: Perform the following baseline assessments

- Assessment of continued eligibility (Refer to [Section 3.1.2](#) and [Section 3.1.3](#))
- Medical history (Refer to [Section 8.4](#))
- Vital signs (Refer to [Section 8.5](#))
- Body Weight (Refer to [Section 8.6](#))
- Physical Examination (Refer to [Section 8.7](#))
- Electrocardiogram (Refer to [Section 8.9](#))
- Urine pregnancy test (Refer to [Section 8.10](#))

- MDS-UPDRS Scale (Refer to [Section 8.11](#))
- Hoehn and Yahr (H&Y) Scale (Refer to [Section 8.12](#))
- Schwab and England (S&E) Scale (Refer to [Section 8.15](#))
- Parkinson's Disease Questionnaire (PDQ-39) total score (Refer to [Section 8.13](#))
- Clinical Global Impression-Severity (CGI-S) scale (Refer to [Section 8.14](#))
- List concomitant medications (Refer to [Section 7](#))
- Columbia-Suicide Severity Rating Scale (C-SSRS) (Refer to [Section 8.16](#))
- Mini-Mental State Examination (MMSE) (Refer to [Section 8.17](#))
- Randomization (Refer to [Section 9.4](#))

Treatment Visit 0 (TV0) – Post Randomization: Perform the following assessments

- Vital signs (Refer to [Section 8.5](#))
- Study treatment dispensation (Refer to [Section 6.7](#))
- Study treatment first dose administration (Refer to [Section 6.7](#))
- Adverse events evaluation after first dose (Refer to [Section 10](#))

